## Safety Assessments

The safety and tolerability assessments will include incidence and intensity of adverse events, withdrawals because of adverse events, physical exams, vital sign measurements and clinical laboratory parameters. Patients in both treatment arms will be followed by a Maternal-Fetal Medicine provider once weekly to ensure continued health and safety of both the subject and the fetus.

### **Ethical and Regulatory Requirements**

This protocol and the associated Informed consent as well as any addenda or amendments, must be reviewed and approved by the Woman's Hospital Foundation Institutional Review Board (WHIRB) review committee and the LSU Institutional Review Board (LSU IRB) prior to the start of the study. Recruitment materials and advertising must be reviewed and approved by the WHIRB and the LSU IRB prior to use. All revisions to this Protocol are considered "protocol amendments" these must be approved in advance, in writing, by the WHIRB and the LSU IRB. Every patient will have given her written informed consent prior to participating in the study. Prior to participation in this trial, each subject will have an opportunity to ask questions and will sign and date a written Informed Consent, which must be witnessed. The signed consent forms will be filed with the investigator's study charts for each subject. A copy of the informed consent will be provided to the subject. Any subject may voluntarily withdraw from the study at any time without prejudicing treatment.

All potential serious breaches must be reported to Woman's Hospital Foundation Institutional Review Board (WHIRB) review committee and the LSU Institutional Review Board (LSU IRB) immediately. A serious breach is a breach of the conditions and principles of GCP in connection with the study or the protocol, which is likely to affect, to a significant degree, the safety or physical or mental integrity of the subjects of the study or the scientific value of the study. Study personnel involved in conducting this

study will be qualified by education, training, and experience to perform their respective tasks. This study will not use the services of study personnel where sanctions have been invoked or where there has been scientific misconduct or fraud (e.g., loss of medical licensure; debarment).

Regarding side effects of the selected treatment method of the treatment arm, overall, side effects are relatively innocuous. The most common treatment-related, adverse effects of macrolides as a group are gastrointestinal effects. Loose stools, diarrhea and abdominal pain are most commonly reported. Azithromycin has been shown to have a greater degree of gastrointestinal tolerance when compared to erythromycin. The most common treatment-related adverse effects of amoxicillin include nausea and vomiting. Other adverse effects of azithromycin include, but are not limited to, anaphylaxis, hypersensitivity reaction, QTc prolongation, cardiac arrhythmias, torsade de pointes, hepatotoxicity, and interstitial nephritis. Overall, azithromycin is well-tolerated with minimal associated side effects. When looking at the benefit-risk assessment, the macrolides demonstrate clinical advantages such as broad coverage for common urogenital microbes, beneficial anti-inflammatory properties, and good tolerability amongst many patients.

The most common treatment-related, adverse effects of amoxicillin include anaphylaxis or hypersensitivity reactions, dermatologic conditions (Stevens-Johnson Syndrome, toxic epidermal necrolysis), and gastrointestinal conditions (*Clostridium difficile* with prolonged use). When prescribed in those with no history of adverse reactions, namely hypersensitivity reactions or dermatologic conditions, amoxicillin is well-tolerated among many. By benefit-risk assessment, benefits of preventing maternal infection and subsequent pregnancy complications outweigh the low-risk nature of associated adverse events/side effects associated with amoxicillin use.

Other treatment-related side effects to be considered within the study includes the potential fetal and maternal outcomes associated with increased latency period, possibly attributable to the administration of said antibiotic course. Potential adverse fetal outcomes of prolonged latency include pulmonary hypoplasia, Potter-like facies, and fetal limb or skeletal deformities. Potential adverse maternal outcomes include intraamniotic infection, endometritis, placental abruption and higher risk of retained placental products following delivery. Other considerations include periviable delivery (23-25 weeks gestational age), as a result of increased latency attributable to antibiotic course, which can be associated with significant morbidity. Survival rates have reportedly ranged from 23-76% when considering delivery at gestational ages from 23 to 25 weeks gestation with associated neurodevelopmental delay reportedly as high as 45%.

To protect the safety of all subjects enrolled in the study, subjects of both arms of the study will be counseled that, if at any point during the study, subjects show signs of infection (fever, rigors, chills, pain), labor, placental abruption (vaginal bleeding), or fetal distress, they are to present to Woman's Hospital's Assessment Center for further evaluation. If, upon further clinical evaluation, the subject is found to be in labor, have signs of chorioamnionitis, have signs of placental abruption or have signs of fetal distress, subject will be admitted to Woman's Hospital for induction of labor/delivery as recommended per established standards of care. Delivering physician will be either the patient's primary obstetrician or MFM specialist if subject received prenatal care at facility outside of Woman's Hospital.

For safety, all subjects who enter the study are evaluable. Subjects will be monitored for safety by assessment of adverse events, physical exams, vital signs and laboratory values. Continued patient safety assessment will be carried out and all adverse events documented and reported to the WHIRB and LSU IRB. On each visit, compliance with treatment will be checked with questions about the side-effects and a subjective evaluation of the tolerability of the administered drug; the patients will also be asked about incidental missed administrations.

Adverse events will be evaluated on a continuous basis while the patient is on study. Patients should be followed until all treatment-related adverse events have recovered to baseline or are deemed irreversible by the principal investigator.

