## **Study Endpoints and Assessments**

### **Primary Endpoint**

The primary efficacy endpoint is the difference in the latency period, defined as the number of days from the date of rupture of membranes to the date of delivery, between those receiving oral, outpatient antibiotic therapy prior to 23 0/7 weeks gestational age and those receiving no antibiotic therapy.

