### **Secondary Endpoint**

The secondary efficacy endpoint is whether the subject reached viability (23 0/7 weeks gestational age) prior to delivery. Comparisons will be made in the difference in the number of patients reaching viability in the control arm (no oral, outpatient antibiotic therapy prior to 23 0/7 weeks gestational age) and the number of patients reaching viability in the treatment arm (oral, outpatient antibiotic therapy prior to 23 0/7 weeks gestational age).

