APPENDIX IV: DATA COLLECTION SHEET

Unique Patient Identifier: \_\_\_\_\_

Date of enrollment: \_\_\_\_\_

Primary OB: \_\_\_\_\_

Insurance: Medicaid      Commercial

Age: \_\_\_\_\_

Race/Ethnicity: \_\_\_\_\_

Gravida: \_\_\_\_\_ Parity: \_\_\_\_\_

History of prior C-section: Y    N    # of prior C-sections: \_\_\_\_\_

Maternal co-morbidities: \_\_\_\_\_

Tobacco use: Y    N

Height: \_\_\_\_\_ Weight: \_\_\_\_\_ BMI: \_\_\_\_\_

EDD: \_\_\_\_\_ EDD as determined by: \_\_\_\_\_

Initial Admission Data

Date of rupture: \_\_\_\_\_ EGA at time of rupture: \_\_\_\_\_

GC/CT/T panel results: \_\_\_\_\_

Wet Prep/ Vaginitis panel results: \_\_\_\_\_

Urinalysis results: \_\_\_\_\_

White blood cell count (WBC) on initial admission: \_\_\_\_\_

MVP on admission: \_\_\_\_\_

Follow-up Data

Date	# of pills	EGA	Weight	BP	HR	RR	Temp	MVP

*\*Attach all ultrasound reports, including those performed in the hospital as well as in during outpatient follow-up in MFM clinic, and copies of MFM dictation reports (H&P, clinic follow up notes, discharge summaries, etc.) within patient's clinical file.*

Delivery Data

WBC on re-admission: \_\_\_\_\_

Date of delivery: \_\_\_\_\_ EGA at time of delivery: \_\_\_\_\_

Latency (days): \_\_\_\_\_

Indication for delivery: \_\_\_\_\_

Fetal gender: \_\_\_\_\_

BMZ course received: Y    N

    If so, complete course received (2 doses received 24hrs apart): Y    N

Neuromagnesium received: Y    N

    If so, number of hours received: \_\_\_\_\_

Standard of care latency antibiotics received on re-admission: Y    N

    Number of days of antibiotic course received \_\_\_\_\_

Chorioamnionitis diagnosed: Y    N

Postpartum follow-up

Endomyometritis: Y    N

Placental pathology: \_\_\_\_\_

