## **PREVIABLE PPRM STUDY**

**OBJECTIVE:** The primary aim of this study is to determine the effect of oral, outpatient antibiotics, when given prior to 23 0/7 weeks gestational age following previable PPRM between 18 0/7 and 22 6/7 weeks gestational age, on pregnancy latency periods. Latency period as defined as the number of days from rupture of membranes to the day of delivery.

**DATE OF STUDY INITIATION:** TBD

**STUDY DURATION:** Dependent on time of enrollment, maximum enrollment time 16 weeks

**BENEFIT OF ENROLLMENT:** Potential prolongation of pregnancy after early rupture of membranes

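### The protocol says fetal and maternal outcomes of longer latency will be considered, but its data sheet records no infant outcome after birth except gender, so a latency gain could not be told apart from a later loss

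*Protocol*

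**What the plan says.** Under Ethical and Regulatory Requirements the protocol sets its own standard: "Other treatment-related side effects to be considered within the study includes the potential fetal and maternal outcomes associated with increased latency period". It then names the outcomes. For the fetus: "Potential adverse fetal outcomes of prolonged latency include pulmonary hypoplasia, Potter-like facies, and fetal limb or skeletal deformities". For the mother: "Potential adverse maternal outcomes include intraamniotic infection, endometritis, placental abruption and higher risk of retained placental products following delivery". It adds periviable delivery, noting "Survival rates have reportedly ranged from 23-76% when considering delivery at gestational ages from 23 to 25 weeks gestation" and neurodevelopmental delay as high as 45%.

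The primary endpoint is "the number of days from the date of rupture of membranes to the date of delivery". The secondary endpoint is "whether the subject reached viability (23 0/7 weeks gestational age) prior to delivery". Neither includes the state of the infant.

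Appendix IV (Data Collection Sheet) has a delivery block: dates, gestational age, latency, indication for delivery, fetal gender, treatments received and chorioamnionitis. A block headed "Postpartum follow-up" holds endomyometritis and placental pathology. Under Methods, each woman has one such sheet, marked with her medical record number and study identifier. The collected data go into a final spreadsheet without the record number, and the paper copies are then shredded.

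**The concern.** The protocol argues that longer latency may itself bring harm and says it will look at this, but the sheet is not built to do so. No later analysis plan can tabulate what was never recorded.

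The stake is interpretation. If antibiotics move deliveries later, both endpoints improve. Whether those pregnancies end in more living infants or in later losses is the next question any reader will ask, and the planned dataset cannot answer it. The gap cuts both ways: it would hide a survival benefit as readily as a harm.

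The gap may also be hard to close afterwards. Once the spreadsheet omits the record number and the sheets are destroyed, the protocol describes no key linking a row to a hospital chart.

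**Working it through.** The plan gives no figure on this point to reproduce, so the check is a count, a comparison of two records, a date calculation and a look at what 17 per arm can show.

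**1. Named outcomes against Appendix IV fields**

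| Outcome named in the protocol | Field in Appendix IV |
|---|---|
| Pulmonary hypoplasia | none |
| Potter-like facies | none |
| Limb or skeletal deformity | none |
| Intraamniotic infection | yes (chorioamnionitis Y/N) |
| Endometritis | yes (endomyometritis Y/N) |
| Placental abruption | none of its own; may appear as indication for delivery |
| Retained placental products | none of its own; placental pathology is partial information |
| Survival after birth at 23 to 25 weeks | none |
| Neurodevelopmental delay | none |

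Dedicated fields: fetal 0 of 3, maternal 2 of 4, neonatal 0 of 2, so 2 of 9 in all. Periviable delivery can be derived from gestational age at delivery.

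**2. What the endpoints can distinguish**

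Take two women with rupture at 20 0/7 and delivery at 24 0/7 (hypothetical). Latency is (24 − 20) × 7 = 28 days for both, and both passed 23 0/7. If one infant lives and the other dies, no structured field on the sheet need differ.

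**3. Whether adverse event reporting fills the gap**

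Adverse Event Procedures defines an AE in a subject who was given the investigational product. Section 1A collects all SAEs until 30 days after dosing stops, and later ones only if believed related to the drug or a protocol procedure. Controls take no study drug, so for them the window has no defined end.

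For the antibiotic arm, assume admission on the day of rupture, randomisation one day later and a 7-day course starting that day:

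window end = rupture + 1 + 6 + 30 days

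- Rupture at 18 0/7 (day 126): 126 + 37 = day 163 = 23 2/7.
- Rupture at 22 6/7 (day 160): 160 + 37 = day 197 = 28 1/7.

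Methods allows pregnancy to continue to 34 0/7 (day 238). The uncovered time can therefore reach 238 − 163 = 75 days or 238 − 197 = 41 days. A woman who delivers earlier has less, or none.

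**4. What 17 per arm can show about survival**

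- With no events in an arm, the one-sided 95% upper limit for the true rate is 1 − 0.05^(1/17) = 16.2%.
- Power for survival of 50% against 76%, two-sided 5%, normal approximation. The 50% is assumed; 76% is the top of the protocol's range. Pooled proportion 0.63; null SE = √(2 × 0.63 × 0.37/17) = 0.166; alternative SE = √((0.50 × 0.50 + 0.76 × 0.24)/17) = 0.159. Then z = (0.26 − 1.96 × 0.166)/0.159 ≈ −0.41, or about 34% power. About 53 per arm would be needed for 80%.

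**The case against.** The strongest reply is that Appendix IV is not the only record. Death and congenital anomaly are SAE criteria, and neither line is limited to the mother. The protocol counts every subject who enters as evaluable for safety and follows treatment-related events to recovery or irreversibility. It also refers to an SAE form, a nonserious AE page and supplemental forms, which are not in the text available. The data sheet itself asks for ultrasound and maternal-fetal medicine reports, including discharge summaries, to be attached in the clinical file.

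Much of this stands. A reader might infer that almost none of the named harms is captured, or that no infant outcome will be recorded for any of the 34 pregnancies. The documents do not support either. Two maternal harms have their own fields, periviable birth is derivable, free text and attached reports give partial information, and some infant deaths or anomalies may reach the SAE file.

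What does not stand is using that route to compare arms. The AE definition does not clearly reach untreated women or newborns, the window has no end for controls, and in treated women it can close weeks before delivery. The attached reports named are maternal and antenatal; no neonatal record is mentioned.

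It is also fair to say that tabulation by arm is commonly left to an analysis plan. That does not answer the point, because Appendix IV fixes what is collected.

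**Conclusion.** The concern holds for the Appendix IV sheet and the dataset built from it. No fetal or neonatal outcome named in the protocol has a field, and abruption and retained placenta have none of their own. Both endpoints measure time in utero only. Followed as written, the plan cannot say whether a latency gain came with surviving infants or later losses.

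The 41 to 75 uncovered days rest on the assumed timing of admission, randomisation and dosing, and on delivery at 34 0/7. They are upper limits for those two rupture dates, not typical values.

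Three further inferences are tempting but unsupported:

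- **A count of unrecorded infant deaths.** This would need the number delivering at 23 to 25 weeks in each arm, which the protocol does not give. The same survival range also implies survivors.
- **Unequal ascertainment of endomyometritis between women.** The protocol sets no date for it, but silence does not show that follow-up differs. Clinic visits end at 23 0/7 because stable women are then readmitted until delivery.
- **That latency may be read only jointly with survival.** Latency is a legitimate stated aim. The point is that infant outcome should be available beside it.

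**What to change.** Add to the Delivery Data block of Appendix IV, identically for both arms:

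- live birth, intrauterine death or intrapartum death;
- infant alive at hospital discharge, with date of death if not;
- pulmonary hypoplasia as diagnosed in the chart;
- limb or skeletal deformity;
- placental abruption Y/N;
- retained placenta Y/N.

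State that these are abstracted from existing hospital records before the paper sheets are destroyed, and reported descriptively by randomised arm beside latency. The endpoints and sample size need not change, and no hypothesis test on survival is asked for.

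The cost is a short chart abstraction for 34 mother-infant pairs, with no new test, visit or change in care. There are two downsides. The dataset can close only after the last infant is discharged, and consent must cover use of the infant's record. The consent form is not in the text available, so whether it already does so should be checked.

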### **Adverse Event Procedures**

An adverse event (AE) is defined as any new untoward medical occurrence or worsening of a preexisting medication condition in a clinical investigation subject administered an investigational (medicinal) product and that does not necessarily have a causal relationship with this treatment. An AE can therefore be any unfavorable and unintended sign (such as an abnormal laboratory findings), symptom, or disease temporarily associated with the use of investigational products, whether or not considered related to the investigational product.

The causal relationship to study drug is determined by a physician and should be used to assess all adverse events (AEs). The causal relationship can be one of the following

- Related: There is a reasonable causal relationship between the study drug administration and the AE.
- Not related: There is not a reasonable causal relationship between study drug administration and the AE.

The term “reasonable causal relationship” means there is evidence to suggest a causal relationship.

Adverse events can be spontaneously reported or elicited during open-ended questioning, examination, or evaluation of a subject. (In order to prevent reporting bias, subjects should not be questioned regarding the specific occurrence of one or more AEs.)

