### **Safety Measures:**

Safety and tolerability will be assessed by collecting data on adverse events (AEs) by patient self-report, weekly laboratory tests, periodic physical examinations with vital signs, and weekly fetal testing via ultrasound in MFM office. Patients will be educated about the side effects azithromycin and ampicillin. Patient's will also be educated on physical monitoring of vaginal bleeding, body temperature, and pelvic pain as it relates to concerns for development of chorioamnionitis, preterm labor, and placental abruption. At weekly follow up visits in the MFM office, patients will be specifically asked about such symptoms if not volunteered. If patient reports any of the aforementioned symptoms or temperature greater than 100.4 degrees Fahrenheit during at home monitoring, patient will be admitted to the hospital for further assessment and possible induction of labor/delivery.

This protocol and the associated Informed Consent as well as any addenda or amendments, must be reviewed and approved by both the Woman's Hospital Institutional Review Board (WHIRB) review committee and LSU Health and Sciences Center of New Orleans, LA Institutional Review Board (LSU IRB) prior to the start of the study. All revisions to this Protocol are considered "protocol amendments"; these must be approved in advance, in writing, by the WHIRB and LSU IRB. Every patient will have given her written informed consent prior to participating in the study. Prior to participation in this trial, each subject will have an opportunity to ask questions and will sign and date a written Informed Consent, which must be witnessed. The signed consent forms will be filed with the investigator's study charts for each subject. Any subject may voluntarily withdraw from the study at any time without prejudicing treatment.

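### The adverse event section bars questions about specific events that the weekly visits require, and side-effect questions tied to the study drug let ascertainment differ by arm

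*Protocol*

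**What the plan says.** Three parts of the protocol govern how women are questioned about adverse events.

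- **Adverse Event Procedures** lists the permitted routes: "Adverse events can be spontaneously reported or elicited during open-ended questioning, examination, or evaluation of a subject". A parenthetical then gives the ban and its purpose: "In order to prevent reporting bias, subjects should not be questioned regarding the specific occurrence of one or more AEs". The same section defines an adverse event to include "any unfavorable and unintended sign (such as an abnormal laboratory findings), symptom, or disease", whether or not it is thought to be related to the product.
- **Safety Measures** opens as the plan for "collecting data on adverse events (AEs) by patient self-report", alongside laboratory tests, examinations and ultrasound. Women are taught "physical monitoring of vaginal bleeding, body temperature, and pelvic pain". At the weekly maternal-fetal medicine visits, "patients will be specifically asked about such symptoms if not volunteered".
- **Ethical and Regulatory Requirements** says that at each visit "compliance with treatment will be checked with questions about the side-effects and a subjective evaluation of the tolerability of the administered drug".

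Study Rationale describes the trial as non-blinded. The control group receives no antibiotics, and no placebo is described.

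**The concern.** One section forbids what another requires. A clinician seeing a woman who has not mentioned bleeding or pelvic pain is told to ask about it under Safety Measures and not to ask under Adverse Event Procedures. What reaches the adverse event record then depends on which section that clinician follows.

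The second issue is separate. Questions about the side effects and tolerability of a drug can be put only to women who have taken it. If they prompt reports in the antibiotic arm with no counterpart in the control arm, the arms are observed differently. The ban is justified as a guard against reporting bias, so the protocol names this hazard and then leaves a route for it.

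At stake is the safety description: Safety Assessments lists the incidence and intensity of adverse events and withdrawals because of them. With no blinding, unequal questioning could look like a drug effect or blur one.

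**Working it through.** The protocol states no adverse event rate and no probability that an event is captured by open or by prompted questioning. There is therefore no figure to reproduce, and the check is textual.

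**Step 1. Are the weekly symptoms adverse events?** Bleeding, fever and pelvic pain are unfavorable signs or symptoms, so they fall within the definition's wide wording. Safety Measures places them in the paragraph that sets out how adverse event data are collected, so the questions cannot simply be treated as clinical care outside that record.

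**Step 2. Do the rules collide?** Under Adverse Event Procedures, "subjects should not be questioned regarding the specific occurrence of one or more AEs". Under Safety Measures, specific questions are mandatory for whatever is not volunteered. The two instructions cover the same women, visits and symptoms. No section gives one precedence or says whether answers to the symptom questions enter the adverse event record. The conflict is direct. Because the weekly questions are not limited to one arm, it makes recording depend on the rule followed, not on arm.

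**Step 3. Where does arm come in?** The compliance check concerns the administered drug, so it can apply only to the antibiotic arm. Two other places point the same way:
- Methods gives counselling on the risks and side effects of the two antibiotics to the treatment arm, while both arms are counselled on warning symptoms.
- The section on nonserious adverse event collection starts the clock at the first study drug, a date that controls do not have.

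**Step 4. What pulls the other way?** Methods gives every woman a pamphlet with a side-effect log, which is copied at each follow-up visit. That source is common to both arms. Safety Measures also describes education on side effects without limiting it to one arm.

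**Step 5. Scale.** Statistical Methods and Sample Size Calculations plans 17 women per arm. One additional woman with a recorded event moves that arm's incidence by 1/17 = 5.9 percentage points. This shows only how sensitive the comparison is to a few reports. It does not estimate how many would be gained or lost.

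**The case against.** The strongest reply has four parts.

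1. **The definition refers to subjects given an investigational product.** Read literally, the ban would not reach controls' symptoms. That would still leave the contradiction in the antibiotic arm, and it would widen the difference between arms. It also fits poorly with the statement under Ethical and Regulatory Requirements that everyone entering the study is evaluable for safety.

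2. **The side-effect questions could be open-ended.** This stands. They need not breach the ban, so the direct contradiction lies only between Safety Measures and Adverse Event Procedures. The arm point survives because even an open question about the drug has no equivalent in the control arm.

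3. **A common source exists.** The log carried by all women reduces the asymmetry, and this also stands. The log does not settle how visit questions are asked or which source prevails.

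4. **Monitoring continues regardless.** A reader might infer that obeying the ban would end weekly screening for infection or abruption. The documents do not support that. Examination and evaluation are expressly permitted, and Methods requires weekly vital signs, physical examination, ultrasound and a blood count in both arms, plus a daily temperature log. Only the verbal symptom questions are in doubt.

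A reader might also expect practice to differ between sites. Weekly follow-up is in one clinic, so the relevant variation is between clinicians.

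**Conclusion.** The contradiction between Adverse Event Procedures and Safety Measures is real and should be corrected. It rests only on the wording of the two sections and on the ordinary reading that the listed symptoms are adverse events.

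The difference by arm is a softer inference. It rests on the side-effect questions being tied to the administered drug in an open-label trial without placebo, and it is partly offset by the common log. Ascertainment can differ by arm; the documents do not establish that it will, or by how much. A reader might want to put a number on it, but any number would rest on capture rates that the protocol does not give.

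Nor should the point be carried over to efficacy. Neither latency nor reaching viability is shown to be affected, and the statistical section states no test of adverse events between arms. The point concerns the quality of the safety record.

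**What to change.** Reconcile the three sections, leaving the clinical symptom monitoring as it is:

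1. Amend the parenthetical in Adverse Event Procedures so that the symptom questions required by Safety Measures are exempt from the ban, and say that the answers enter the adverse event record.
2. State one questioning procedure for every visit, identical in both arms: an open question first, then the same symptom questions for every woman whatever her allocation.
3. Take side-effect questions out of the drug-compliance check and put them into that common procedure. Pill counts and missed doses can stay in the compliance check.
4. Record for each event whether it was volunteered or prompted, so that the two can be tabulated separately.

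This costs a protocol wording change and a short form used at visits already scheduled. Recorded adverse event counts may rise in both arms. It is best done before enrollment, because events elicited unequally cannot be made comparable afterwards.
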